## 5.3 Exclusion Criteria

The presence of any of the following will exclude a subject from enrollment:

1. Known hypersensitivity or allergy to posaconazole or other azole antifungal agents
2. Concomitant medications primarily metabolized by CYP3A4 including (***but not limited to***):
  - a. HMG-CoA inhibitors primarily metabolized by CYP3A4 (increases risk of rhabdomyolysis)
  - b. Sirolimus
  - c. Ergot alkaloids
  - d. Vincristine
  - e. upadacitinib
3. Proarrhythmic conditions
4. Moderate or severe renal impairment (Cr Clearance  $<50$ )
5. Elevated transaminases or bilirubin  $> 2.5x$  ULN.
6. Current diagnosis of ulcerative colitis, indeterminate colitis, ischemic colitis, infectious colitis, or microscopic colitis.
7. Fulminant colitis, toxic megacolon, peritonitis, ileostomy or colostomy.

CONFIDENTIAL

This material is the property of Cedars-Sinai Medical Center.

8. Stool sample positive for pathogens including ova and parasites, *Salmonella*, *Shigella*, and *C. difficile* at screening.
9. History of any clinically significant neurological, renal, hepatic, gastrointestinal, pulmonary, metabolic, cardiovascular, psychiatric, endocrine, hematological disorder or disease or any other medical condition that, in the Investigators opinion, would prevent the subject from participation in the study.
10. Treatment with antibiotics, antifungal agents, probiotics, or prebiotics within two weeks of screening.
11. Alcohol or drug abuse (in the opinion of the Investigator) that would interfere with compliance.

#### **5.4 Subject Recruitment and Screening**

Potential study candidates will be identified from the Cedars-Sinai Inflammatory Bowel Disease Center genetic database (MIRIAD) and Mayo Clinic's IBD Biobank; all MIRIAD and Biobank participants have previously provided written, informed consent to participate in genetic research and to be contacted for potential research opportunities. Patients who have CARD9 risk allele will be notified of an opportunity to participate in this trial at the time of a routine clinical encounter, if deemed appropriate by their treating provider. They will be provided with information about the study, and if the study candidate is interested in study participation, they will be scheduled for the screening visit.

Patients who wish to participate in this research, who have not previously had their CARD9 risk allele testing performed or who are not in MIRIAD or Mayo Clinic's IBD Biobank, will have an opportunity to provide a blood sample for genetic testing of CARD9, once Informed Consent to participate has been provided.

At the screening visit, patients will be asked to provide informed consent for the study. A complete medical history will be taken including list of current and recent medications. A complete physical examination, including height, weight, vital signs will be performed. Safety laboratory studies, pregnancy test, stool studies, and EKG will be performed at this visit (stool may be provided after the visit). Chest radiography will be performed. Then, patients meeting eligibility will be scheduled for baseline colonoscopy. Patients meeting eligibility criteria will be scheduled for the baseline visit.

#### **5.5 Lifestyle guidelines**

Patients will be instructed to continue their current dietary and exercise patterns during the trial, excluding non-prescription supplements or herbal preparations which might affect hepatic metabolism.

#### **5.6 Early withdrawal of Subjects**

##### **5.6.1 When and How to Withdraw Subjects**

Subjects may be withdrawn from study for safety concerns, progression of Crohn's disease (requiring new medication or escalation of dose of current therapies, hospitalization, or surgery), withdrawal of consent, failure to adhere to protocol requirements, patient request, or administrative reasons. Withdrawal may be warranted at the request of the patient, investigator, or study protocol. The reason for study withdrawal will be determined by the investigator. Patients will be required to return all remaining study therapy.

The data from subjects who withdraw consent will continue to be used in analysis before the date of withdrawal of consent, however no follow-up or inquiries will be conducted on these patients on or after this date.

If a subject does not attend a scheduled visit, the subject will be called three times at the number provided by the subject. Subjects who do not answer will be sent a certified letter. The record of these contacts and any written communication will be included in the study documentation. Subjects who do not respond to these inquiries will be assigned as lost to follow-up (LTFU).

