| Transcriptomics Endpoints           | 
 
Changes in stool and mucosal washing metabolites
 
Changes in microbiome / metabolome reflected in gene expression patterns in mucosal biopsies
 
  |

|                                    |  |
|------------------------------------|--|
| 
Statistical
Methodology
 | 
The primary analysis population will be the intention-to-treat population. The primary efficacy endpoint and key secondary endpoints will also be analyzed with the per-protocol population. The primary and key secondary endpoints will be evaluated using descriptive statistics, Exact Fisher's and t-test to compare treated vs placebo-controlled subjects. . In the case of missing clinical data, the missing data points will be treated by non-responder imputation.
 
The primary endpoint is endoscopic response, defined as a 50% reduction SES-CD scores at week 12. Each patient will be scored on a binary response (improved/not improved). We will assume the placebo response rate of approximately 10% . We estimate that a study size of 24 patients is necessary, assuming a drop-off rate of ~10% before the second colonoscopy, to yield final analysis of at least 11 subjects per arm. With a final sample size of 22 subjects, we will have 76% power to detect a difference of 0.50 in the rate of response for treatment with posaconazole therapy vs placebo from the assumed underlying placebo response rate at the 0.05 significance level in a Fisher's Exact Test. This assumes the treatment response rate will be 0.70h or greater.
 
Secondary endpoints will include clinical remission (defined as Crohn's disease activity index < 150), analysis of data regarding use of corticosteroids, mucosal healing, mucosal improvement, normalization of inflammatory biomarkers, and improvement in health-related quality of life. Repeated measures analysis will be used to examine changes over time from baseline. Categorical data will be analyzed with repeated measures logistic regression while continuous measures will use mixed modeling regression. Residuals will be inspected to confirm data meets assumptions necessary for parametric testing. Data will be considered significant at the two-sided p-value of <0.05. All analysis will be performed by the study biostatistician ([name], MS) using SAS v9.4 software.
 |
|------------------------------------|--|

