### **5.6.2 Data Collection and Follow-up for Withdrawn Subjects**

Subjects with early withdrawal from study during the twelve-week intervention period, for any reason, will be scheduled for a safety follow-up visit four weeks from date of withdrawal. Subjects who withdraw from study after the intervention period will maintain the per-protocol final follow-up visit at week 36. The clinical outcome will be assessed at this follow-up visit.

Subjects with abnormal laboratory findings, or other adverse events requiring early study withdrawal, will be followed until the abnormality has resolved to baseline or steady state. The investigators will determine if the adverse event was related to study therapy. The clinical course will be documented.

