### **6.4 Subject Compliance Monitoring**

Subjects need to keep the capsule containers and bring them to follow up visit. Compliance will be evaluated by the counts of unused tablets. If a deviation from protocol is identified, the investigators will inquire as to the reason for study deviation during the corresponding patient encounter. Non-compliance related to study medication regimen and (i.e., less than 80% or more than 120% of recommended dosing) and not due to adverse events will be evaluated by the Investigator who will encourage subject to follow the medication regimen prescribed. Patients who remain significantly non-compliant with the drug regimen and not due to adverse events for two consecutive visits will be withdrawn from study or earlier at the discretion of the PI. The subject will then complete the final follow-up visit per protocol.

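### Persistent non-adherence ends study participation rather than study drug alone, so the SES-CD is taken off schedule with no rule for using it; separately, the follow-up rules after consent withdrawal conflict

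*Combined protocol and SAP*

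**What the plan says.** **Leaving the study.** Section 5.6.1 gives one list of reasons why a subject may be withdrawn from the study. Besides safety and disease progression it names "withdrawal of consent, failure to adhere to protocol requirements, patient request, or administrative reasons". Section 6.4 is firmer on study drug: "Patients who remain significantly non-compliant with the drug regimen and not due to adverse events for two consecutive visits will be withdrawn from study". The thresholds there are below 80% or above 120% of recommended dosing, and the principal investigator may act sooner. It adds: "The subject will then complete the final follow-up visit per protocol".

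**Outcome and analysis.** The primary endpoint (Section 4.2) is endoscopic response by SES-CD at Week 12. The Synopsis states: "The primary analysis population will be the intention-to-treat population". Section 9.3 defines that population as everyone who took at least one dose. The Synopsis also says that missing clinical data are handled by non-responder imputation; Section 9 does not repeat this.

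**Early termination.** Footnote 1 of Table 1 and Section 7.4 require the Week 12 procedures, colonoscopy included, at the time of discontinuation or soon after. Section 7.4 also places unblinding after those evaluations.

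**Consent withdrawal.** After consent is withdrawn, Section 5.6.1 says that "no follow-up or inquiries will be conducted on these patients on or after this date". Section 5.6.2 says: "Subjects with early withdrawal from study during the twelve-week intervention period, for any reason, will be scheduled for a safety follow-up visit". Section 4.1 schedules the same four-week visit, and Section 5.6.2 keeps the Week 36 visit for those who leave after the intervention period. None of these carries an exception for withdrawn consent.

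**The concern.** An intention-to-treat comparison at Week 12 needs each treated subject's Week 12 outcome, whether or not the subject kept taking drug. The plan has only one status for a persistently non-adherent subject: out of the study. A rule triggered after randomisation therefore ends scheduled observation of subjects whose Week 12 colonoscopy could have been done. The analysis must then use an earlier score or an imputed failure, and the plan does not say which. With 12 subjects per arm, that choice for one or two people can decide the result.

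The consent conflict is operational. For a subject who withdraws consent, a site cannot follow both Section 5.6.1 and Section 5.6.2.

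**Working it through.** **1. How far off schedule the score can be.** Visits are every two weeks (Section 7.3). Two consecutive non-compliant visits could be Weeks 2 and 4, so mandatory withdrawal can come as early as Week 4, which is 12 - 4 = 8 weeks before the endpoint. The early-termination SES-CD would then be a Week 4 score. The follow-up visit four weeks after withdrawal coincides with Week 12 only if withdrawal is at Week 8. Section 7.6, whose heading also covers the final follow-up after early termination, lists another colonoscopy, so a second score may exist. Nothing in Section 9 says which score, if any, is the Week 12 value. The imputation sentence speaks of clinical data without saying whether endoscopy is included.

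**2. The plan's own power figure.** Inputs from Section 9.1: 11 per arm, 10% against 70%, Fisher's exact test at 0.05; two-sided per Section 9.2. Power is the sum of P(X = x) × P(Y = y) over all outcomes with Fisher p ≤ 0.05, where X ~ Bin(11, 0.7) and Y ~ Bin(11, 0.1). Result: 75.5%, with actual level 0.0017. The plan states 76% and 0.002, so it is reproduced.

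**3. Effect of following rather than imputing.** The documents give no non-adherence rate. Assume k = 1 or 2 of 12 per arm are withdrawn for non-adherence, with 70% and 10% response among the rest.

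- Imputed: X ~ Bin(12 - k, 0.7), Y ~ Bin(12 - k, 0.1), each out of 12.
- Followed: X ~ Bin(12 - k, 0.7) + Bin(k, r), Y ~ Bin(12, 0.1), where r is the assumed response of non-adherent drug-arm subjects.

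| k per arm | Imputed | Followed, r = 10% | r = 40% | r = 70% |
|---|---|---|---|---|
| 1 | 75.5% | 74.7% | 78.7% | 82.6% |
| 2 | 66.7% | 64.9% | 74.2% | 82.6% |

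Against imputation, the change runs from 64.9 - 66.7 = -1.8 points to 82.6 - 66.7 = +15.9 points. With nobody affected, power at 12 per arm is 82.6%.

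Imbalance between arms matters too: with two imputed in the drug arm only, power is 61.5%; with two in the placebo arm only, 85.9%.

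**4. Sensitivity to one subject.** For 7/12 against 1/12, one tail is (C(12,7)·12 + C(12,8)) / C(24,8) = (9504 + 495) / 735471 = 0.0136, doubled for equal arms to p = 0.027. For 6/12 against 1/12 it is (924·12 + 792) / C(24,7) = 11880 / 346104 = 0.0343, doubled to p = 0.069. Reclassifying one drug-arm subject crosses 0.05.

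**5. Consent rules side by side.**

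| Case | Section 5.6.1 | Sections 5.6.2 and 4.1 |
|---|---|---|
| Consent withdrawn during the 12 weeks | no contact from that date | visit four weeks later (5.6.2: whatever the reason) |
| Consent withdrawn after Week 12 | no contact from that date | 5.6.2: Week 36 visit kept |

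The two columns cannot both be followed in either row.

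**The case against.** Several objections are sound, and they limit the point.

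- A reader might infer that the plan treats non-adherence, leaving the study and withdrawing consent as one event. It does not: they are separate reasons in one list, consent withdrawal and loss to follow-up have their own text in Section 5.6.1, and drug non-compliance has its own rule in Section 6.4.
- A reader might infer that non-adherent subjects have no outcome or drop out of the analysis. Table 1 footnote 1 and Section 7.4 require the colonoscopy at early termination, and Section 9.3 keeps every dosed subject in the denominator.
- A reader might infer that the early score is discarded, or that the result no longer compares arms as assigned. No section says it is discarded. Counting withdrawal as failure is a recognised composite strategy that still compares randomised arms.
- The power loss is not established. Section 9.1 already allows two dropouts, and one imputed per arm gives the stated 76%. Two per arm for non-adherence alone would double that all-cause allowance, and the +16 also needs 70% response in subjects who dosed poorly.
- Removal could differ by arm because Section 6.4 exempts non-adherence due to adverse events. That is possible, but treatment is masked and the documents give nothing to quantify it.

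What remains is that there is no status for stopping drug while staying in follow-up, no rule says how an early SES-CD is used, and the consent conflict is literal.

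**Conclusion.** The point holds as a minor, inexpensive improvement. Sections 5.6.1 and 6.4 end study participation for persistent non-adherence, which replaces an on-schedule Week 12 SES-CD with an early one of undefined standing in the primary analysis. The subjects stay in the intention-to-treat denominator; the loss is the observed outcome at the planned time.

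The size is uncertain. Under one or two affected per arm and response of 10% to 70% among those in the drug arm, power changes by about -2 to +16 points relative to imputation. If the early score were counted instead, the difference cannot be worked out from the documents. The main gain is less reliance on imputed or off-schedule values, not assured power.

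The consent conflict between Section 5.6.1 and Sections 5.6.2 and 4.1 needs no assumption, and the passages must be reconciled.

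**What to change.** 1. In Sections 5.6.1 and 6.4, separate stopping study drug from leaving the study. Subjects taken off drug for non-adherence or administrative reasons who still consent stay in follow-up and have the planned Week 12 assessments at Week 12. The Week 12 colonoscopy takes the place of the early-termination one, and the blind is kept until then. The rule for when drug is stopped is left as it is. Align the permissive wording of 5.6.1 with the mandatory wording of 6.4.
2. In Section 9, for subjects who do leave early, state how an early-termination SES-CD enters the primary analysis and whether non-responder imputation covers endoscopy. Cross-refer the visits in Table 1 footnote 1 and Sections 5.6.2, 6.4, 7.4 and 7.6.
3. Reconcile Section 5.6.1 with Sections 5.6.2 and 4.1 for subjects who withdraw consent, including the Week 36 visit. Word the exception so that subjects withdrawn for safety, disease progression or any other reason keep the follow-up they have now.

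Cost: protocol wording, and sites follow a few non-adherent subjects to Week 12. Power may fall slightly if those subjects respond at the placebo rate.

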### **5.6.2 Data Collection and Follow-up for Withdrawn Subjects**

Subjects with early withdrawal from study during the twelve-week intervention period, for any reason, will be scheduled for a safety follow-up visit four weeks from date of withdrawal. Subjects who withdraw from study after the intervention period will maintain the per-protocol final follow-up visit at week 36. The clinical outcome will be assessed at this follow-up visit.

Subjects with abnormal laboratory findings, or other adverse events requiring early study withdrawal, will be followed until the abnormality has resolved to baseline or steady state. The investigators will determine if the adverse event was related to study therapy. The clinical course will be documented.

### **5.7 Open Label Posaconazole:**

At 12 weeks, subjects will undergo colonoscopy and clinical assessment for response, after which they will be unblinded. Subjects who meet criteria for active disease AND who are determined to have received placebo will be eligible to receive 12 weeks of open-label posaconazole. Eligibility Criteria for open label posaconazole:

1. Endoscopically-confirmed active Crohn's disease with active disease defined by SES-CD  $\geq 6$  ( $\geq 4$  if ileal only) based on local reading, AND
2. Active symptoms of Crohn's disease (CDAI  $>220$ ), AND
3. Received placebo during the 12-week induction period

Subjects who meet the above criteria and opt to receive open label posaconazole will be monitored for safety / adverse events at follow-up visits. Changes in corticosteroid dosing will be permitted after 12 weeks, regardless of whether subjects are receiving posaconazole or not. All subjects will undergo colonoscopy at 36 weeks.

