### 4.1 General Design

This study is designed as a two-center, placebo-controlled induction trial in 24 subjects with active Crohn's disease, who demonstrate at least one CARD9 S12N risk allele. Expected duration of participation is forty weeks. This will include screening period up to four-weeks and a twelve-week, double-blind induction period.

- Subjects who complete the 12-week induction period, meet criteria for active disease, AND upon unblinding at 12 weeks are determined to have received placebo during the 12-week induction period will be eligible to receive open-label posaconazole for 12 weeks, followed by a 12-week follow-up period.
- Subjects who complete the 12-week induction period and do not meet criteria for active disease, OR upon unblinding at 12 weeks are determined to have received posaconazole during the 12-week induction period will have a follow-up period of twenty-four weeks.

Clinical remission will be defined as the proportion of subjects with endoscopic improvement, defined by a decrease in 50% of the SES-CD endoscopic score. Subjects experiencing early withdrawal from study will be scheduled for a safety follow-up visit four weeks after the date of withdrawal.

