# **5 Subject Selection and Withdrawal**

Subjects (n=24) will be individuals with active Crohn's disease (SES-CD  $\geq 6$  AND PRO2 score of abdominal pain  $\geq 2$  OR PRO2 daily stool frequency  $\geq 4$ ) despite use of conventional therapy. Subjects will be randomly assigned to receive posaconazole or placebo in 1:1 fashion. In this 40-week trial, subjects assigned to treatment will be administered posaconazole (Noxifil®, Merck) 300mg daily for 12 weeks. and then observed off posaconazole over the next 24 weeks. In addition to the treatment intervention, subjects also will provide samples for parallel translational studies including blood for genetic analysis, stool samples for biomarker and microbial composition analysis, and biopsies for mucosal gene expression analysis. Patients meeting criteria for active disease at 12 weeks will be offered open-label posaconazole for 12 weeks and will continue all study-related visits and procedures until final safety visit at week 36.

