## 5.2 Inclusion Criteria

1. Male or female patients  $\geq 18$  years of age.
2. A diagnosis of CD with minimum disease duration of 6 months with involvement of the ileum and/or colon documented on colonoscopy
3. Have an endoscopically-confirmed active Crohn's disease with active disease defined by SES-CD  $\geq 6$  ( $\geq 4$  if ileal only), AND active symptoms of Crohn's disease (CDAI  $>220$ )
4. Subjects receiving oral aminosalicylates (at a stable dose for 2 weeks prior to baseline), immunomodulators (at a stable dose for 4 weeks prior to baseline), anti-TNF, anti IL12/23, or anti-integrin therapy (at stable maintenance doses for  $\geq 8$  weeks) may continue their use during the study.
5. Subjects receiving oral corticosteroids may continue their use during the study provided the dose (prednisone up to 20 mg/day, budesonide up to 9 mg/day) has been stable for two weeks prior to screening.
6. Lab findings of hypokalemia, hypomagnesemia, or hypocalcemia are eligible, provided electrolyte abnormalities are corrected and stable prior to study enrollment.
7. Have had age-appropriate and disease-duration-appropriate colon cancer screening without unresected dysplasia.
8. Women of childbearing age, excluding those with prior bilateral tubal ligation or at least one-year post-menopause, must not be pregnant, lactating, or planning to become pregnant. They must agree to use effective contraception throughout the study period.
  - a. Option 1: Any one of the following highly effective methods: hormonal contraception for example, birth control pills, injection, implant, transdermal patch, vaginal ring); intrauterine device (IUD); tubal ligation (tying your tubes); or a partner with a vasectomy
  - b. Option 2: Any two of the following effective methods: male or female condom PLUS one of the following additional barrier methods (a)diaphragm with spermicide; (b) cervical cap with spermicide; or (c) contraceptive sponge with spermicide
9. Subjects must be able to provide informed consent and understand, agree with, and be able to adhere to daily diary entries, all scheduled visits, tests, procedures, and protocol in English.

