#### **7.4 Week 12 ( $\pm 3$ days) or early termination**

This visit may be conducted within three days of the specific time-point marking the number of weeks since baseline visit. The following tasks will be conducted at these visits:

- Assessment of concomitant medications.
- Complete physical examination, vital signs, and weight.
- Laboratory studies: urine pregnancy test in women of childbearing potential, serum posaconazole concentration, hsCRP, serum chemistries, complete blood count with automatic differential, lipid panel, and stool calprotectin, microbiome, blood for transcriptomics.
- 12-lead EKG.
- Study therapy usage reviewed.
- Adverse event monitoring.
- Review of bowel movement diary.
- Calculation of CDAI and PRO2 scores
- IBDQ and SF-36 assessments.
- Colonoscopy with biopsies (RNALater & Formalin) and washings scheduled  $\pm 7$  days of this visit for calculation of SES-CD. Biopsies and washings should be obtained from same area of each region as screening samples.
- Following the above evaluations, subjects will be unblinded and determined to have received either posaconazole or placebo during the 12-week induction period.
- Patients meeting criteria for active disease AND who are determined to have received placebo will be eligible to receive open label posaconazole; these subjects will be dispensed 4 weeks posaconazole at this visit.

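### Open-label entry at Week 12 applies no laboratory limit, and at best an ambiguous QTc limit, before a placebo subject's first posaconazole dose

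*Combined protocol and SAP*

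**What the plan says.** Section 5.7 gives the rule for open-label drug: "Subjects who meet criteria for active disease AND who are determined to have received placebo will be eligible to receive 12 weeks" of posaconazole. It then lists three criteria, all required: SES-CD of at least 6 (at least 4 if ileal only) on local reading, CDAI above 220, and placebo during induction. Safety appears in 5.7 only as monitoring at the follow-up visits.

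The other statements of the rule are no stricter on safety. Section 4.1 adds completion of induction and says that subjects with active disease who "are determined to have received placebo during the 12-week induction period will be eligible to receive open-label posaconazole for 12 weeks". The opening of Section 5 mentions disease activity alone: "Patients meeting criteria for active disease at 12 weeks will be offered open-label posaconazole for 12 weeks". Section 7.4 orders the visit as tests first, then "Following the above evaluations, subjects will be unblinded", and for those who qualify "these subjects will be dispensed 4 weeks posaconazole at this visit".

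The pre-exposure limits stand elsewhere and are tied to entry. Section 5.3 opens: "The presence of any of the following will exclude a subject from enrollment". It covers proarrhythmic conditions (3), creatinine clearance below 50 (4) and transaminases or bilirubin above 2.5x ULN (5). Inclusion 6 in Section 5.2 admits low potassium, magnesium or calcium "provided electrolyte abnormalities are corrected and stable prior to study enrollment". The synopsis adds a QTc limit of 460 msec on the baseline EKG.

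**The concern.** For a placebo subject, the open-label dose is the first exposure to posaconazole. The trial decided that certain liver, renal, electrolyte and cardiac findings should bar first exposure. It wrote that decision for the start of the blinded phase and did not repeat it where first exposure can happen again, after at least 12 further weeks of active Crohn's disease. A subject whose Week 12 potassium or ALT would have kept them out at baseline meets every listed open-label criterion.

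What is at stake is subject safety and consistent handling at two sites. The protocol treats QTc prolongation as a safety endpoint (Section 4.4). Its own table in Section 2.3.1 reports hypokalemia in 22% and hypomagnesemia in 10% of subjects on 300 mg daily, though in a non-comparative study of immunocompromised patients. Starting the drug with an uncorrected electrolyte deficit is the situation inclusion 6 was written to prevent.

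**Working it through.** This is a check of text; the plan states no figure to reproduce. The question is whether any provision carries each pre-exposure limit forward to the Week 12 dispensing decision.

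| Limit | Where set | Applies to | Tested at Week 12? | In the open-label rules (4.1, 5, 5.7, 7.4)? |
|---|---|---|---|---|
| Transaminases/bilirubin >2.5x ULN | Exclusion 5 | Enrollment | Yes, chemistries | No |
| Creatinine clearance <50 | Exclusion 4 | Enrollment | Yes, creatinine in chemistries | No |
| Electrolytes corrected and stable | Inclusion 6 (no numeric cut-off) | Before enrollment | Yes, safety labs | No |
| QTc >460 msec | Synopsis, exclusion 3; Section 5.3 gives no number | Baseline EKG | Yes, 12-lead EKG | No |
| QT >450 ms (men), >460 ms (women) | Section 8.4 | No visit named, no action stated | Yes, 12-lead EKG | No |

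**Does an eligibility assessment fall at Week 12?** Table 1 marks one at screening and one at baseline, and footnote 3 describes only those two. Section 7.4 lists none. Section 7.6 does list one at Week 36, where no drug follows. In Appendix 6, the compliance officer's eligibility review is tied to enrollment and study entry.

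**How many subjects?** Section 5 states: "Subjects will be randomly assigned to receive posaconazole or placebo in 1:1 fashion". With 24 subjects, 24 x 1/2 = 12 on placebo. Section 5.1 mentions no blocking, so about 12 is the right description. Only those with active disease who choose open label would be dosed. The documents give no rate of out-of-limit results at Week 12, and none is assumed.

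**When is the next scheduled check after dosing?** Section 7.5 places chemistries, and the EKG for open-label subjects, at Week 16. If drug is dispensed at the Week 12 visit, that is Day 112 - Day 84 = 28 days. With both 3-day windows, the range is 109 - 87 = 22 to 115 - 81 = 34 days. In the blinded phase, chemistries recur every 2 weeks (Section 7.3). Scheduled laboratory monitoring after first exposure is therefore sparser in open label, which gives the Week 12 decision more weight.

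**The case against.** The best counter-text is Section 8.4, which says EKG findings must not show prolonged QT and is not limited to screening. A Week 12 EKG is required before unblinding, so 8.4 can be read as a QTc gate. That reading is arguable: 8.4 sits beside the screening chest X-ray requirement, is not cited in 5.7 or 7.4, and states no consequence. For men it conflicts with the synopsis (450 against 460). It is enough to prevent a flat claim that QTc is unguarded. It does nothing for liver, renal or electrolyte results.

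Discretionary safeguards also exist. Section 5.6.1 permits withdrawal for safety concerns, 5.6.2 contemplates withdrawal for abnormal laboratory findings, and 10.2 gives the principal investigator safety oversight. Because 4.1 requires completed induction, a subject withdrawn on those grounds never reaches open label. These provisions soften the gap, but none sets a threshold. The synopsis describes open label as something a subject may enroll into, which might be said to re-trigger the exclusions. Section 5.7's own explicit list makes that reading weak.

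A further objection concerns the remedy. In Section 7.2, baseline chemistries are drawn and drug is dispensed at the same visit, and 6.3 has the first dose observed there. Nothing makes blinded dosing wait for same-visit results, so requiring Week 12 laboratory results in hand would be stricter than the gate being copied. This stands, and the fix allows for it.

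**Conclusion.** The gap is real for liver, renal and electrolyte results, and QTc is ambiguous. Followed as written, the open-label rules admit to first exposure subjects whom the trial's own entry limits would bar. About 12 subjects could reach the decision; the number affected is unknown. The conclusion rests on reading 5.7's list as complete, which its heading as eligibility criteria supports.

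Stronger readings are not supported:

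- A reader might infer that open-label dosing would rest on old test results. Section 7.4 requires chemistries and an EKG at Week 12, before unblinding; the missing part is a pass/fail rule.
- A reader might infer a dosing error in renal or hepatic impairment. Section 2.2.3 recommends no dose adjustment for mild to moderate renal impairment or for any grade of hepatic impairment. For those tests the issue is consistency with the trial's own limits.
- A reader might infer damage to the efficacy result. The Week 12 endpoints are assessed before open-label drug is given and are unaffected.

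This merits correction as a matter of subject safety, but it is modest in scale.

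**What to change.** Add a fourth criterion to Section 5.7, mirrored in 4.1, the opening of 5, and 7.4. Before open-label drug is dispensed, the Week 12 EKG and the most recent available safety laboratory results must meet exclusions 3-5 and inclusion 6. Use Week 12 laboratory results if they are back, otherwise Week 10. If Week 10 results are used, review the Week 12 results promptly and stop drug if they are out of limits.

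State one QTc limit for this check. The sponsor can choose the synopsis limit (above 460 msec for all) or the sex-specific limits in 8.4. Add a Week 12 eligibility assessment to Table 1 and 7.4 for these subjects.

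No new test is needed. The cost is that a few subjects may be delayed or may not enter open label. The EKG must be read before dispensing, and Table 1 footnote 9 assigns that reading to non-study physicians. Some waiting may exist already: criterion 1 depends on a colonoscopy that 7.4 allows up to 7 days after the visit, and the CDAI in criterion 2 needs a hematocrit.
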